### Data Analysis Plan for Hypothesis 3a:

*Hypothesis 3(a): Participants who are exposed to YRI will demonstrate greater reduction in mental health and functional problems than participants who do not receive the YRI intervention; emotion regulation (as measured using the Disturbances in Emotion Regulation Scale) will operate as a major mechanism of YRI improvements; high comorbidity will be a treatment modifier.*

**Primary Outcomes** DERS, HSCL, OMPA Externalizing, WHODAS

**Primary Predictors:** Time (baseline, Post-YRI, Post-ENTR, and 12 months and group membership (Control, ENTR, ENTR + YRI).

**Possible Moderators:** Subject gender, age, education level/literacy, session attendance

**Strata Indicators:** Subject ID and Cluster ID. With only three geographic/political districts, an insufficient number to constitute a level in multilevel modeling, the districts will be introduced at the top level (i.e., the clusters) as fixed effects by means of dummy variables to account for any district effects.

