## **Part II Emotion Regulation as the Mechanism Through which the YRI improvements operate**

**Primary Outcomes:** OMPA internalizing, OMPA externalizing

**Primary Predictor:** Group Membership (Control, ENTR-only, YRI+ENTR)

**Hypothesized Mediator:** Emotion Regulation (assessed by DERS)

**Possible Moderators:** Subject gender, age, education level/literacy, session attendance

We hypothesize that the YRI improvements may operate through changes in emotion regulation. This is a proposed mediation model where the primary predictor is group membership, the primary outcome is mental health at 12 months, and the mediator is emotion regulation as measured by the Difficulties in Emotion Regulation (DERS) at six weeks. We will test for the indirect effect of group membership on Mental Health Status using conditional process analysis (Hayes, 2013). The conditional process equations are (if gender modifies the indirect effect for example):

$$DERS(6\ weeks) = B_0 + a * X$$

$$MH(12\ months) = B_0 + cX + b_1 * DERS(6\ weeks) + b_2 * G + b_3 * G * DERS.$$

Where  $X$  is group membership and  $G$  is gender. The coefficient  $a$  quantifies the effect of group membership on emotion regulation and  $b$  quantifies the effect emotion regulation on mental health independent of group membership. The product  $p = a(b_1 + b_3 * G)$  is the *indirect effect* of group membership on Mental Health. We can test for the significance (null hypothesis  $p = 0$ ) via

bootstrapping. A significant (at 0.05) is indication that emotion regulation mediates the relationship between the YRI effects and mental health. For outcomes that are binary we will need to use the KHB method (Breen, Karlson, & Holm, 2013) to rescale the regression coefficients correctly. A strength of this analysis is that group membership, emotion dysregulation and Mental Health are measured at three different time points which is necessary for causal mediation (though not sufficient).

As an alternative we can test for mediation using Structural Equation Modeling (SEM). This approach is more flexible than conditional process analysis and may allow us to use full-information maximum likelihood (FIML) as opposed to multiple imputation. All causal models will be evaluated for the possible effects of unmeasured confounders (VanderWeele & Ding, 2017).

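### The Part II mediation test cannot separate an effect through emotion regulation from correlated early change in symptoms that persists to 12 months

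*Combined protocol and SAP*

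**What the plan says.** All of this is in the combined protocol and SAP.

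- **Mediator equation** (Part II of the Hypothesis 3a plan): "DERS(6\ weeks) = B_0 + a * X", where X is group.
- **Outcome equation** (same place): "MH(12\ months) = B_0 + cX + b_1 * DERS(6\ weeks) + b_2 * G + b_3 * G * DERS", where G is gender.
- **Outcomes in Part II**: "OMPA internalizing, OMPA externalizing".
- **Decision rule**: the product of the two paths is bootstrapped, and "A significant (at 0.05) is indication that emotion regulation mediates the relationship between the YRI effects and mental health".
- **Timing argument**: "A strength of this analysis is that group membership, emotion dysregulation and Mental Health are measured at three different time points", followed at once by the caveat "which is necessary for causal mediation (though not sufficient". The section also promises a sensitivity evaluation for unmeasured confounders and offers SEM as an alternative.
- **Baseline adjustment**: the cluster-matching section requires a baseline aggregate of the outcome at cluster level in every analysis. The Hypothesis 3a plan says individual-level confounders will be assessed but names none.
- **Waves**: the Hypothesis 3a plan first lists "Time (baseline, Post-YRI, Post-ENTR, and 12 months", with outcomes "DERS, HSCL, OMPA Externalizing, WHODAS". Later in the same plan each participant has three measurements: baseline, post-training and 12 months. The label six weeks appears only in Part II and is not tied to either list.

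**The concern.** Randomization protects the path from group to DERS. It does not protect the path from six-week DERS to 12-month mental health, because participants are not randomized to their DERS score. Within an arm, youth with worse six-week DERS are likely to have worse six-week symptoms, and those symptoms carry forward. With six-week mental health left out, b_1 absorbs that carry-forward even if DERS has no effect on symptoms. Multiply it by a real YRI effect on DERS and the product can be significant without any mediation.

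At stake is the part of Hypothesis 3(a) that calls emotion regulation a major mechanism of the YRI. The randomized comparison of arms over time is not affected.

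**Working it through.** The plan gives no figure to reproduce: it states no sample size, effect size, SD, correlation or power. Its only relevant number is the 0.05 level. Everything below except that level and the form of the equations is an assumption.

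**Set-up.** Two arms, SD units, gender terms and clustering ignored, and no effect of DERS on mental health:

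- DERS6 = a·X + e1
- MH6 = g·X + e2, with corr(e1, e2) = r
- MH12 = rho·MH6 + e

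**Closed form for the printed model.** Given X, the coefficient on DERS6 is cov(e1, rho·e2)/var(e1), so b_1 = r·rho. The false indirect effect is a·r·rho. The early symptom gain g does not appear; the cX term takes it up. As a share of the total effect g·rho, the false part is a·r/g, which equals r when a = g.

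**Simulated false-mediation rates** (a = g = −0.3; 500 to 1,000 replicates per setting; a 95% Monte Carlo interval for the product stands in for the bootstrap):

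| r | rho | b_1 = r·rho | a·r·rho | 100 per arm | 200 per arm | 400 per arm |
|---|---|---|---|---|---|---|
| 0.3 | 0.3 | 0.09 | −0.027 | 13% | 33% | 71% |
| 0.3 | 0.5 | 0.15 | −0.045 | 33% | 73% | 98% |
| 0.5 | 0.3 | 0.15 | −0.045 | 32% | 71% | 98% |
| 0.5 | 0.5 | 0.25 | −0.075 | 52% | 85% | 99% |

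Mean simulated b_1 and products agree with the closed form (for r = rho = 0.5: b_1 of 0.248 to 0.252, products of −0.074 to −0.078). With MH6 added to the outcome equation, the rate in these twelve cells is 2% to 6% and mean b_1 is about 0.

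**What drives it.**

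- r = 0: 1% to 6%. It stays at 4% with a larger early gain, g = −0.6.
- a = 0: about 5%.
- g = 0, r = rho = 0.5, 200 per arm: still 85%.
- Smaller effects, a = g = −0.15, r = rho = 0.3, 200 per arm: 11%.

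**Does individual baseline adjustment cure it?** (200 per arm)

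- If six-week changes are themselves correlated (r = 0.3, rho = 0.5): 69% as printed, 67% with baseline DERS and mental health.
- If the correlation is only a stable baseline trait: 56% as printed, 4% with the baselines.

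**Is adding MH6 neutral?**

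- True lagged DERS effect of 0.20 with r = rho = 0.5: the printed model gives 0.20 + 0.25 = 0.45; with MH6 it gives 0.20.
- True DERS effect already complete within the six-week wave (0.4 on MH6, carried forward by rho = 0.5, 400 per arm): the real indirect effect is −0.3 × 0.4 × 0.5 = −0.060. The printed model finds it 99% of the time. With MH6 added, the estimate is 0.000 and detection falls to 5%.

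**The case against.** The best case for the plan has four parts.

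**The plan already concedes the limit.** It says temporal order is not enough and promises an unmeasured-confounder evaluation. That tempers interpretation, and a reader who infers that the plan treats three time points as proof goes too far. But neither provision changes the equation or the 0.05 rule. Mental health at the mediator's wave is a variable the trial may have measured, so it should be modelled rather than left to a sensitivity value.

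**The printed equations are not the whole model.** They are illustrative for gender, and cluster-level baseline aggregates are required everywhere. This is fair. Even so, a cluster aggregate does not remove correlation between individuals' DERS and symptoms within arms, and no section names six-week mental health or individual baselines for this test.

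**Adjusting for six-week mental health can hide a true mechanism.** This stands in full. The variable is post-randomization, is measured alongside the mediator, and may lie on the causal path. A reader might infer that emotion regulation should count as a mechanism only if it survives that adjustment. The last calculation shows why that does not follow.

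**The data may not exist.** This stands in part. The outcome list for the repeated waves has OMPA Externalizing but not internalizing, and the number of waves is inconsistent.

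**Conclusion.** The point holds as a limit on what Part II can show. As specified, a significant product is compatible both with mediation through DERS and with correlated early change that persists. The false component is about a·r·rho. It needs a YRI effect on six-week DERS, a within-arm correlation between DERS and symptoms, and persistence to 12 months.

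Three stronger readings are not supported:

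- **That any lasting early symptom gain will be reported as mediation.** The gain itself is absorbed by the group term. With r = 0 or a = 0 the false rate is nominal.
- **That the rates apply to this trial.** They ran from nominal to about 99% (11% to 99% in the correlated settings with a YRI effect on DERS), depending on assumed n, effect, r and rho. Clustering and the third arm were left out. A false share of about half the total effect only restates an assumed r of 0.5 with equal effects on both scales.
- **That baseline adjustment is useless.** It removes the problem when the correlation is a stable trait, and not when six-week changes are correlated. The documents do not say which applies.

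This is a cheap improvement to a mechanism analysis. It does not undermine the main group comparison.

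**What to change.** 1. Put individual baseline DERS and the individual baseline value of the outcome in both mediation equations, alongside the cluster aggregates already required.
2. Prespecify two estimates of the DERS-specific indirect effect: one without and one with the mental health measure from the mediator's wave. Use OMPA Externalizing, and OMPA internalizing if it is collected then. Enter it as a parallel mediator in the same bootstrap, or use a cross-lagged SEM.
3. State the reading in advance. If the two agree, say so. If they disagree, report that the data do not separate DERS mediation from joint early improvement. Do not let the adjusted model alone decide, because it removes any DERS effect that had already reached mental health by that wave.
4. Reconcile the four-wave and three-wave descriptions in the Hypothesis 3a plan, say which wave is six weeks, and say whether both OMPA subscales are collected then. If one is not, state that its mechanism test lacks the second estimate.

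The cost is SAP wording and a few model terms. No new data collection is needed where the scale is already collected at that wave. The price of showing both estimates is that the answer may be openly inconclusive.

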### **Data Analysis Plan for Hypothesis 3b:**

*Hypothesis 3(b): Improvements in mental health and functioning due to YRI will lead to (mediate) greater employment outcomes and superior economic self-sufficiency over time.*

**Primary Outcome:** Measures of employment and superior economic sufficiency.

**Primary Predictor:** Group membership.

**Mediator:** Mental Health as measured by the HSCL, OMPA; functioning as measured by WHODAS

**Possible Moderators:** Subject gender, age, education level/literacy, session attendance

Similar to Aim 3(a) we will test for mediation using condition process analysis the process equations are similar:

$$MH(12\ months) = B_0 + a * X$$

$$Employment = B_0 + B_0 + cX + b_1 * MH + b_2 * G + b_3 * G * MH$$

The indirect effect of mental health on employment and economic self-sufficiency is quantified by the product  $p = a(b_1 + b_3 * G)$ . We will use a bootstrap test to access significance. Binary outcomes will need to be adjusted using KMB method. The size and direction of effects will be determined by the estimates of the regression coefficients.

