### **Data Analysis Plan for Hypothesis 3c:**

*Hypothesis 3(c): Homelessness, orphanhood, young parenthood, and high problems in emotion regulation comorbid with other mental health conditions will be moderators lessening the effectiveness of YRI.*

**Primary Outcome:** Measures of employment and superior economic sufficiency

**Primary Predictor:** Group Membership

**Mediator:** Mental Health

**Possible Moderators:** Subject gender, age, education level/literacy, session attendance, emotion regulation.

To the mediation model described in hypothesis 3b we will add terms to account for the moderating influences of gender, age, education level/literacy, session attendance, and emotion regulation. For purposes of exposition we will generically label the moderator as  $W$ . Our hypothesis is that moderators act on the influence of group membership and mental health. The conditional process equations in this case are (only one moderator was included for brevity):

$$MH(12\ months) = B_0 + a * X$$

$$Employment = B_0 + B_0 + cX + b_1 * MH + b_2 * G + b_3 * G * MH$$

In these equations the indirect effect of group membership on employment and economic self-sufficiency is  $(a_1 + a_3 * W) * b$ . The value  $a_3 * W * b$  is sometimes called the index of moderated mediation. In the case of dichotomous  $W$  (gender, homelessness, young parenthood) this value reduces to  $a_3 * b$  and is interpreted as the difference of the indirect effect of group membership on employment and economic self-sufficiency of the two  $W$  groups. Test for moderation can be directly from the coefficient  $a_3$ . Alternative tactics include SEM as opposed to conditional process equations. KHB rescaling will be needed since moderators, mediators, and outcomes represent different variable types (binary, continuous etc.). In practice we can include all moderators in the model simultaneously.

We can also verify which path the candidate variables modify (we assumed the path from primary predictor to mediator). This can be done in the context of SEM models. We can fit models where the moderators act on the paths from mediator to outcome or both. Using fit indices such RMSEA we can compare model fits to determine which model best matches the data.

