**Missing Data:** Using ITT principle we will obtain estimates of missing values of all study participants and at all time points. We will primarily use multiple imputations through chained equations. Missing data may exist at items within scales and we will use the Plumptre method (ref needed). Furthermore, where supported by our software, we can combine the use of imputations with attrition weighting. We will report both percentage of missing data and percentage of complete cases. For SEM models we can employ FIML to address missingness .

**Multiple Comparisons:** We will use False Discovery Rate (FDR) (ref needed) to adjust for multiple comparisons within hypothesis. This is necessary since we will be comparing multiple models.

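### H3b names three mediator scales but specifies a one-mediator model; applied scale by scale, it can credit a scale that has no effect on employment

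*Combined protocol and SAP*

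**What the plan says.** The 3b section of the plan gives the mediators as "Mental Health as measured by the HSCL, OMPA; functioning as measured by WHODAS". That is three scales for two constructs, and the table of outcomes, predictors, moderators and mediators under Aim 3 also lists them as separate hypothesised mediators. The outcome equation printed for 3b is "Employment = B_0 + B_0 + cX + b_1 * MH + b_2 * G + b_3 * G * MH", preceded by one mediator equation for MH at 12 months. "The indirect effect of mental health on employment and economic self-sufficiency is quantified by the product" p = a(b_1 + b_3·G), and "We will use a bootstrap test to access significance". The level is stated for the parallel analysis in Part II of 3a: "A significant (at 0.05) is indication that emotion regulation mediates the relationship between the YRI effects and mental health". The 3b section calls its own approach similar.

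Three other places bear on whether the scales enter together:

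- The 3c section repeats the one-mediator equations and says "In practice we can include all moderators in the model simultaneously". Nothing comparable is said of mediators.
- Part II of 3a offers a different route: "As an alternative we can test for mediation using Structural Equation Modeling (SEM"). The 3c section also mentions SEM. Neither place says that several mediators enter one model.
- The Multiple Comparisons paragraph applies a false discovery rate "to adjust for multiple comparisons within hypothesis. This is necessary since we will be comparing multiple models".

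**The concern.** The hypothesis concerns a pathway made up of several measures, but the model has room for one. The plan does not say how HSCL, OMPA and WHODAS become MH, or where functioning enters.

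The likeliest use of the template is to insert each scale in turn. Under H3a, YRI is expected to reduce both mental health and functional problems, so each scale left out is itself expected to be moved by treatment. If it also affects employment and correlates with the scale that was kept, it confounds the fitted path from mediator to employment.

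Two things are at stake. A scale with no effect on employment could be reported as a mediator, so the trial could not say whether mental health or functioning does the work. And no one estimate would measure the pathway that 3b describes, although 3b is the plan's account of how YRI reaches employment and self-sufficiency, both listed as primary outcomes.

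**Working it through.** **Inputs.** From the plan: three mediator scales, one mediator term, a product test, and level 0.05 (taken as two-sided, since sidedness is not given). The plan states no sample size, effect size or inter-scale correlation, so there is no figure of its own to reproduce. Assumed for illustration: one two-arm contrast X; each scale scored in the same direction with unit residual variance; common residual correlation ρ; continuous outcome; no clustering; no gender term.

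**Step 1: the one-mediator slope.** Let M_k = a_k·X + e_k and Y = c·X + Σ b_k·M_k + error. Given X, regressing Y on M_j alone gives

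b_j* = b_j + ρ × (sum of the other b_k),

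and the reported indirect effect is a_j·b_j*.

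**Step 2: one active scale.** Take a = 0.3 for all three scales and b = (0.3, 0, 0). An inert scale should receive 0. It receives 0.3 × ρ × 0.3:

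- ρ = 0.3: 0.3 × 0.09 = 0.027
- ρ = 0.5: 0.3 × 0.15 = 0.045
- ρ = 0.7: 0.3 × 0.21 = 0.063

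The active scale's true effect is 0.3 × 0.3 = 0.090.

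**Step 3: how often an inert scale is declared a mediator.** Simulation with 1,000 runs per cell and direct effect c = 0.1. A 95% Monte Carlo interval for the product stands in for the bootstrap.

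| ρ | One-mediator, n = 400 | One-mediator, n = 800 | Joint model, n = 400 | Joint model, n = 800 |
|---|---|---|---|---|
| 0 | 5% | 7% | 5% | 8% |
| 0.3 | 34% | 68% | 4% | 5% |
| 0.5 | 69% | 97% | 4% | 5% |
| 0.7 | 86% | 98% | 5% | 5% |

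With all three scales in one outcome equation, the joint indirect effect averaged 0.088 to 0.091 against a truth of 0.090.

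**Step 4: all scales active.** Take a = 0.3 and b = 0.2 for each, so the true joint effect is 3 × 0.3 × 0.2 = 0.180. One scale alone gives 0.3 × (0.2 + ρ × 0.4):

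- ρ = 0.3: 0.096, or 53% of the truth
- ρ = 0.5: 0.120, or 67%
- ρ = 0.7: 0.144, or 80%

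Here a single scale overstates its own share (0.060) and understates the joint pathway.

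**Step 5: when the problem shrinks or vanishes.**

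- ρ = 0: no bias.
- A scale that YRI does not move (a = 0): no credit.
- Inert scales moved less, a = 0.2 and 0.1: credit of 0.018 to 0.042 and 0.009 to 0.021 over the same ρ.
- ρ = −0.3, a = 0.3: the credit changes sign, to −0.027.
- All b_k = 0: the added term is ρ × 0 = 0, so no scale is credited.

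**The case against.** **The equations are templates.** The plan introduces gender as an example, says that only one moderator is shown for brevity, and writes out employment while applying the product to self-sufficiency too. Mental health measured by HSCL and OMPA could also mean one construct with two indicators, and SEM is available. This stands in part: a reader might infer that the plan commits to one model per scale, and it does not say so. But no composite or latent factor is defined, functioning is still a second mediator, and SEM is an option without a stated model. Nor would an unstated composite be safe. With equal a, the mean of the three scales recovers 0.090. With a = 0.3, 0.2 and 0.1 and only the first scale active, it gives 0.2 × 0.3 = 0.060 against 0.090.

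**Adding the effects.** A reader might infer that 3b would overstate the total effect, since separate effects sum to 1 + 2ρ times the truth when a is equal: 1.6, 2.0 and 2.4 at ρ = 0.3, 0.5 and 0.7. The plan nowhere proposes to add effects across scales, so this is not an error in it.

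**False support for 3b.** A reader might also infer that 3b could be declared true when nothing mediates. Under this mechanism it would not be: an inert scale is credited only because another named scale truly works. The randomised group comparisons are untouched.

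**Safeguards in the plan.** False discovery rate control acts on error rates and does not remove bias in a slope. The check for unmeasured confounders does not adjust for co-mediators that were measured.

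**A joint model has limits.** This stands. If YRI moves HSCL, HSCL moves WHODAS, and WHODAS moves employment, the one-mediator HSCL estimate is right as the effect passing through HSCL. In a simulated chain at n = 800 it was 0.054, while the joint model's HSCL-specific effect was 0.000. DERS is also a hypothesised mediator elsewhere in the plan but is not among those named for 3b. If only DERS were active (a = b = 0.3, ρ = 0.5), each joint slope would be 0.3 × 0.5 / (1 + 2 × 0.5) = 0.075, and the three scales together would be credited with 3 × 0.3 × 0.075 = 0.0675.

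**Conclusion.** The concern holds as a mismatch between hypothesis and model: 3b names three mediator scales, the specified model carries one, functioning is in no equation, and no joint model is given. Applied scale by scale, the template can name the wrong scale as mediator, and no single-scale estimate equals the 3b pathway in general.

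The direction follows from algebra wherever the scales are positively correlated and moved by YRI, and at least one of them affects employment. The size is illustrative only: 0.027 to 0.063 credited to an inert scale, against 0.090 for the active one, rests on assumed effects, correlations, a continuous outcome and no clustering. The harm is misattribution and mis-sizing within an explanatory analysis.

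**What to change.** In the 3b section of the plan:

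1. Replace the outcome equation with one containing every named mediator score (HSCL, the OMPA score or scores to be specified, and WHODAS) and each score's gender interaction. Give one mediator equation per score. The OMPA choice must be explicit, because Part II of 3a separates internalizing from externalizing and 3b does not.
2. Make the bootstrapped joint indirect effect the 3b test: Σ a_k(b_k + b_3k·G), evaluated at each level of G, or Σ a_k·b_k if the interaction is dropped.
3. Report scale-specific effects from that same model as secondary. Note that they depend on the causal order of the scales, so a scale that acts through another can show no specific effect.
4. Keep single-mediator models, if wanted, as descriptive. Label them as not separating the scales and not to be summed.

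The cost is SAP wording, slightly more programming, and wider intervals for the scale-specific effects because the scales overlap. The joint effect does not depend on how the scales are ordered. No new data are needed.

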**Youth FORWARD scale-up study AIM 3:**

**AIM 3 (Clinical Effectiveness):** To compare clinical effectiveness of YRI when delivered via the EPP platform to results of our previous randomized control trial (RCT) of YRI as measured by improved mental health and reduced functional impairments among high-risk youth. Emotion regulation will be examined as a major mechanism by which the YRI improves behavior of treated youth and their functioning in the ENTR.

*Hypothesis 3(a): Participants who are exposed to YRI will demonstrate greater reduction in mental health and functional problems than participants who do not receive the YRI intervention; emotion regulation (as measured using the Disturbances in Emotion Regulation Scale) will operate as a major mechanism of YRI improvements; high comorbidity will be a treatment modifier.*

*Hypothesis 3(b): Improvements in mental health and functioning due to YRI will lead to (mediate) greater employment outcomes and superior economic self-sufficiency over time.*

*Hypothesis 3(c): Homelessness, orphanhood, young parenthood, and high problems in emotion regulation comorbid with other mental health conditions will be moderators lessening the effectiveness of YRI.*

The table below outlines study primary outcomes, primary predictors, moderators and hypothesized mediators.

Primary Outcome Variables
Difficulties in Emotion Regulation (DERS)
Hopkins Symptom Checklist (HSCL)
Oxford Measure of Psychosocial Adjustment (OMPA)
Employment
Economic Self-Sufficiency
Primary Predictor Variables
Time
Group Membership (ENTR-only, YRI+ENTR, Control)
Possible Moderators
Gender
Age

Education Level
Literacy
Session Attendance
Hypothesized Mediators
Emotion regulation (DERS)
Oxford Measure of Psychosocial Adjustment (OMPA)
Hopkins Symptom Checklist (HSCL)
WHO Disability Assessment Scheduled (WHODAS)

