The goal of this analysis is to determine if there are differences among the three groups assigned at randomization (Control, ENTR, and ENTR+YRI). As described above, all analyses will include the aggregated baseline value of the outcome as a control at the cluster level, and furthermore, of any cluster-level potential treatment confounders shown to be imbalanced across the three groups. In particular we will be looking for group differences in the slopes of the primary outcomes over the lifetime of the study. Fixed effects will be time and group membership and their two-way interaction. Each subject will be measured three times—baseline, post-training, and at 12-month follow up—so we have three repeated measures for each subject, and each set of repeated measures is nested within study cluster. Subject- and cluster-specific slopes and intercepts will be modeled as random effects. We can test for the necessity of the subject and cluster specific slopes through likelihood ratio tests. Evidence of a group differential effects will be if the likelihood ratio test for the time by group interaction is significant at the 0.05 level. For pairwise differences we will examine the regression coefficients and base inference on Wald tests. We will estimate the model with Restricted Maximum Likelihood (REML, also MLR) for testing for random effect parameters and Full Maximum Likelihood (FML or MLF) for fixed effects. We will account for attrition by calculating inverse probability weights and/or multiple imputation. All linear modeling assumptions will be verified, both by

evaluating underlying distributions and model residuals. Approaches to the violation of model assumptions or for non-continuous outcomes include use of response transformations, generalized linear mixed effect models or generalized estimating equations.

We now expand the above model to include possible effect modifiers gender, mental health status at baseline. To the model above we will include a three-way interaction between time, gender, and treatment group. Evidence of a moderating effect will be if likelihood ratio test for the three-way interaction term is significant at the 0.05 level.

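### Employment and economic self-sufficiency are listed as primary outcomes, but this Aim 3 plan specifies no estimate or test of the total effect of assignment on them

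*Combined protocol and SAP*

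**What the plan says.** The table in the section on Aim 3 lists five primary outcome variables: DERS, HSCL, OMPA, employment and economic self-sufficiency.

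The arm comparison is in the Data Analysis Plan for Hypothesis 3a. Its purpose is plain: "The goal of this analysis is to determine if there are differences among the three groups assigned at randomization". Evidence of a differential effect is that the "likelihood ratio test for the time by group interaction is significant at the 0.05 level". The heading of that section names its own primary outcomes, "DERS, HSCL, OMPA Externalizing, WHODAS". Neither economic outcome is among them.

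Employment and self-sufficiency are taken up in the section for Hypothesis 3b, which states that "Improvements in mental health and functioning due to YRI will lead to (mediate) greater employment outcomes and superior economic self-sufficiency over time". The method is given as follows: "Similar to Aim 3(a) we will test for mediation using condition process analysis the process equations are similar". One equation regresses 12-month mental health on group (coefficient a). The other regresses employment on group (c), mental health (b1), gender (b2) and their product (b3). The quantity tested, by bootstrap, is p = a(b1 + b3·G). The section adds that "The size and direction of effects will be determined by the estimates of the regression coefficients".

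The 3c section puts moderators into the same mediation model, on the path from group to mental health, with the path from mental health to outcome, or both, as alternatives.

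**The concern.** Randomisation protects one quantity for employment: the difference between arms as assigned, that is, the total effect. The plan for the two economic outcomes stops short of it. The product p contains b1, an association between two variables that are both observed after randomisation. The coefficient c is the group difference with a post-randomisation mediator held fixed. Neither is the randomised comparison.

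The product can therefore be clearly positive when employment is the same in the arms, if a direct effect in the other direction cancels it or if mental health and employment share an unmeasured cause. It can also be null when assignment raises employment by a route that the mental health and functioning scales do not capture. In either case a reader who asks whether YRI changed employment has no planned result to turn to. The 3c section inherits the gap, because moderation of the direct path, and so of the overall effect on employment, is not among the options it names.

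**Working it through.** The plan gives no sample size, effect size or standard deviation, so there is no figure of its own to reproduce. The check has two parts.

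**Tracing each primary outcome in the Aim 3 table to an analysis**

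| Outcome | Arm comparison headed for it | Other planned test |
|---|---|---|
| DERS | yes (3a) | mediator in 3a Part II |
| HSCL | yes (3a) | mediator in 3b |
| OMPA | externalizing only (3a) | outcome in 3a Part II, mediator in 3b |
| Employment | none | indirect product (3b, 3c) |
| Economic self-sufficiency | none | indirect product (3b, 3c) |

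Substituting the first 3b equation into the second, for a linear model, gives

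total effect at G = c + a(b1 + b3·G).

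The plan tests the second term. It names no test of c, and no estimate, contrast or decision rule for the sum.

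**How far the product and the total can part**

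All inputs here are assumptions: two arms of n independent youths (no clustering), a continuous outcome, residual SD 1, no gender term.

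Zero total effect: a = 0.3, b = 0.2, c = −0.06, so c + ab = −0.06 + 0.06 = 0. The standard errors are SE(a) = √(2/n) and SE(b) ≈ 1/√(2n). Power of the product is approximated by requiring both a and b to be significant, Φ(a/SE(a) − 1.96) × Φ(b/SE(b) − 1.96).

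| n per arm | a/SE(a) | b/SE(b) | Product significant | Simulated |
|---|---|---|---|---|
| 100 | 2.12 | 2.83 | 0.564 × 0.807 = 46% | 42–45% |
| 200 | 3.00 | 4.00 | 0.851 × 0.979 = 83% | 83% |
| 400 | 4.24 | 5.66 | 0.989 × 1.000 = 99% | 99% |

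The total-effect test rejects in about 5%, its nominal level.

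Effect that bypasses the mediator: a = 0, b = 0.2, c = 0.25, so the product is 0 and the total is 0.25. The outcome SD is √(1 + 0.2²) = 1.02 and SE(total) = 1.02·√(2/n).

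| n per arm | SE(total) | 0.25/SE | Power, total effect | Simulated, total | Simulated, product |
|---|---|---|---|---|---|
| 100 | 0.144 | 1.73 | 41% | 42–43% | 3–6% at all three sizes |
| 200 | 0.102 | 2.45 | 69% | 69–70% | |
| 400 | 0.072 | 3.47 | 93% | 93–95% | |

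A wider set of settings was simulated with a percentile bootstrap, as the plan proposes (500 trials per setting, 400 resamples; n = 150, 300 or 400; a = 0.2, 0.3 or 0.5; total effect always zero). The zero came either from an offsetting direct effect (b = 0.3, c = −ab) or from b = c = 0 with a shared unmeasured cause loading 0.5 on mediator and outcome. The product was significantly positive in 44% to 100% of trials, and the total effect was significant in 3% to 6%. With a harmful total effect (a = 0.3, b = 0.3, c = −0.2; 0.09 − 0.20 = −0.11; n = 400) the product was still significantly positive in 99%.

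**The case against.** The strongest reply is that Hypothesis 3b is a mediation hypothesis. Its subject is the improvement in mental health and functioning due to YRI, and an indirect effect is the natural estimand for that sentence. This stands. A reader might infer that 3b is simply a claim about the total effect and must fail without a significant one. The wording does not support that, and nothing in the plan says that a significant product will be reported as an employment gain. What remains is that these two outcomes are designated primary and receive no other analysis.

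A reader might also infer that, in the bypass case, the plan would report no benefit. That goes too far: c is in the employment equation and would be estimated, so a direct effect would be visible. But it has no planned test, and it is conditional on the mediator.

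The 3a text speaks of slopes of the primary outcomes, and it allows generalized linear mixed models or estimating equations for non-continuous outcomes. That could be stretched to the Aim 3 table, and it shows that the machinery is at hand. The 3a heading, however, sets its own list of four. The evaluation for unmeasured confounders promised in 3a Part II is a real safeguard for the path from mediator to outcome, but it does not show whether the arms differed. KHB is cited for rescaling coefficients, not to report a total effect.

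Two limits also stand. The document covers Aim 3 only, so the gap is in this plan and not necessarily in the whole study. And exact cancellation is a special case; the documents do not say that YRI delays work.

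**Conclusion.** The point holds for this Aim 3 plan. Followed as written, it produces no randomised total-effect estimate or test for two of the five outcomes that its own table calls primary. That rests on the text alone and needs no numerical assumption.

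The percentages show only that the product and the total effect can disagree, and how often they might. They depend on assumed effects and arm sizes and on a continuous outcome. They also ignore clustering in a cluster-randomised trial; any intracluster correlation would lower the detection rates. They do not predict this trial, and they are not evidence that YRI has no effect on employment or that the sponsor intends to claim one.

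**What to change.** In the 3b section, ahead of the mediation, state that the effect of assignment on employment and on economic self-sufficiency will be estimated for YRI+ENTR versus ENTR-only, and for each versus Control, with the cluster-accounting model of the 3a section. Use a generalized linear mixed model if the outcome is binary. The plan does not say when the economic outcomes are measured, so name the time point and allow a single-time-point version if they are not measured repeatedly. Keep the cluster-level baseline control that the plan already requires in all analyses, and add individual baseline work variables where they were collected. The matching section lists income-generating activities and days and hours worked; it does not list income itself.

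Report total, direct and indirect effects together. State that any conclusion that YRI increased employment rests on the total effect, and that the indirect effect is evidence on mechanism. A significant total effect need not be a gate for the mediation analysis.

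In the 3c section, add a group-by-moderator term to the same total-effect model. Include all these tests in the false discovery rate family for the hypothesis.

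The cost is some wording and a few further models. The downside is a few more tests in that family and a more demanding basis for an employment claim.
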